During the 8-week intervention period, PWD will participate in SaH sessions through the Social Engagement Portal. Data on engagement and affect will be collected during SAFE at Home sessions using the MPES. In addition, PWD will answer questions related to satisfaction at the end of each session.

Post-Treatment/Distal Measures:

The DEMQOL, GDS-SF, ULS, and NPI-NH will be re-administered at Post-Intervention, allowing us to investigate possible long-term effects. Changes on these longer-term measures are not expected in this Phase 1 study.

[figure not shown]
This App will be considered successful if (1) At least 85% of PWD agree to take part in 80% of the sessions; (2) mean session length is at least 25 minutes; (3) PWD exhibit higher levels of positive engagement/affect and lower levels of negative engagement during SaH sessions, as compared to baseline (based upon the MPES); and (4) PWD report high satisfaction with the app, defined as 85% being satisfied or very satisfied.

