- a. This study will use the MPES in this study to examine engagement and affect of PWD. The MPES is an observational scale that measures four types of engagement: Constructive Engagement: motor/verbal behavior exhibited clearly in response to the target activity; Passive Engagement: listening/watching a target activity; Distracted Engagement: motor/verbal behavior exhibited in response to something other than the target activity; and Non-Engagement / Apathy: outward signs/indicators of apathy, such as sleeping, closing one's eyes, and staring into space. The MPES also measures Pleasure, defined as clearly observable smiling or laughing.
- b. For the Phase I study, we will use a large database of participants engaging in activities as the baseline MPES scores. An independent samples t-test will be conducted to examine differences.
 - 0. ~~If a person has not been seen in group activities after three visits and/or if a staff member has told us the person does not attend group activities, we will consider the person a “chronic non-activity attender.”~~
 - 1. ~~We will then target this person in particular in future visits.~~
 - 2. ~~We will ask staff to invite up to three non-attenders per activity.~~
 - 3. ~~If the person attends, we will observe them in the activity.~~
 - 4. ~~If they do not attend, we will go to the person’s room during the session and find out if they are awake or asleep (knock on the door).~~
 - 0. ~~If they are awake, it will be coded as DID OTHER for more than half.~~
 - 1. ~~If they are asleep, it will be coded as SLEPT/CLOSE EYES for more than half.~~
- c. Please note: all MPES observations will be conducted via a HIPAA compliant Google Form. Submitted responses will automatically be sent to a database. As such, there will be no need to save a corresponding PDF file in each participant's digital binder for each MPES observation. To prevent changing of data in the database, there will be a lock on the database preventing changing of data, except by the PI or Experimental Team Leader. Although each MPES observation will not have a corresponding PDF file in the participant's digital binder, a PDF will be generated for each observation for auditing purposes. The PDFs will be placed in a single folder. MPES observations will be spot checked for accuracy by comparing database data to PDF form data.

Intervention Period Data Collection

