**SAFE at Home: A Service to Provide Social Engagement to
Community-Dwelling Persons With Dementia**

NCT05516147

Statistical Analysis Plan

12/1/23

The SAFE at Home app will be considered successful if persons with dementia exhibit higher levels of positive engagement/affect and lower levels of negative engagement- as measured by the Menorah Park Engagement Scale (MPES)-during the intervention, as compared to known means for standard programming. Multiple observations of participants will be taken during SAFE at Home programming. Then, means will be calculated for each participant for each item (on the MPES) or positive and negative subscale (for the EPWDS). Then, we will conduct a one-sample *t*-test to determine whether there are significant differences between the known means and the means observed during SAFE at Home programming. We will also conduct paired sample *t*-tests to examine whether participants exhibit an improvement in the Dementia-Related Quality of Life Scale (DEMQOL), Geriatric Depression Scale – Short Form (GDS-SF), Neuropsychiatric Inventory – Nursing Home (NPI-NH), and the UCLA Loneliness Scale (ULS).

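### Success on the MPES has no defined positive and negative score and no rule for combining the item tests, so the same data can give different verdicts

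*SAP*

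**What the plan says.** Protocol 1.0 lists four success criteria for the app. The third is that "PWD exhibit higher levels of positive engagement/affect and lower levels of negative engagement during SaH sessions, as compared to baseline", judged on the MPES. The SAP repeats it as its only success condition: participants are to "exhibit higher levels of positive engagement/affect and lower levels of negative engagement- as measured by the Menorah Park Engagement Scale (MPES)-during the intervention", measured against known means for standard programming.

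On scoring, the SAP states that "means will be calculated for each participant for each item (on the MPES) or positive and negative subscale (for the EPWDS"). On testing, it states that "we will conduct a one-sample *t*-test to determine whether there are significant differences between the known means and the means observed" in the programme. It gives no number of tests, alpha level or sidedness, and no way to turn several results into one verdict.

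Protocol 7.0, item 7, describes the scale: "The MPES is an observational scale that measures four types of engagement" (constructive, passive, distracted, and non-engagement or apathy), and "The MPES also measures Pleasure, defined as clearly observable smiling or laughing". That makes five domains. The text attaches neither a positive nor a negative label to any of them. Under the intervention-period observations, 7.0 plans averages by type of engagement or affect, whereas 9.0 speaks of one average score for the programme. Neither section defines a composite.

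**The concern.** The success statement concerns two quantities, positive and negative engagement, and the scoring plan produces neither for the MPES. The only instrument given such subscales is the EPWDS. It is absent from the measures in Protocol 7.0, the schedule in 8.0, the procedures in 9.0 and the forms list in 14.0.

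Deleting the EPWDS clause would not close the gap. An analyst following the SAP exactly would hold up to five item-level tests and would still have to decide which domains belong to which side, and how many on each side must be significant. If those choices are made after the data are seen, the SAP's only stated success verdict can depend on them.

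**Working it through.** **Which parts of the rule are written down**

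| Element | Status |
|---|---|
| Both halves needed (positive up and negative down) | Stated in Protocol 1.0 and the SAP |
| Participant mean per MPES item | Stated in the SAP; computable |
| Side to which each of the five domains belongs | Not stated |
| Any or all items within a side | Not stated |
| Alpha, sidedness, multiplicity | Not stated |
| Positive and negative subscales | Stated for the EPWDS only |

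The plan gives no power or error figure for this criterion, so there is nothing to reproduce.

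**Effect of any versus all**

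From the documents: n = 12 completers (Protocol 1.0). Assumed: two-sided 5% with success only in the favourable direction (2.5% per test), normal data, an equal standardised effect d on four items (constructive, pleasure, distracted, non-engagement), and a common correlation of 0, 0.3 or 0.6.

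Power for one item at d = 0.89, from the noncentral t with 11 degrees of freedom and noncentrality 0.89 × √12, is 0.801. At correlation 0:

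- Any positive and any negative: (1 − 0.199²)² = 0.92.
- All four: 0.801⁴ = 0.41.
- Two composites, each the mean of two items: the composite effect is 0.89 / √((1 + 0)/2) = 1.259, with power 0.977. Both significant: 0.977² = 0.955.

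For correlations 0.3 and 0.6 the values come from simulation (100,000 runs):

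| Rule, d = 0.89 | Corr. 0 | 0.3 | 0.6 |
|---|---|---|---|
| Any positive and any negative | 0.92 | 0.89 | 0.85 |
| All four items | 0.41 | 0.49 | 0.57 |
| Both composites | 0.955 | 0.88 | 0.82 |

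At d = 0.6 the first two rules give 0.52 to 0.50 and 0.05 to 0.20.

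**False positives**

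With no effect anywhere, any-and-any succeeds in at most about 1.4% of runs and both composites in under 1%. If one side truly improves and the other does not, the both-composites rule cannot exceed the 2.5% of the test on the null side.

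**Passive engagement**

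The definition is "Passive Engagement: listening/watching a target activity", which could be read as positive or as neutral. Suppose constructive engagement and pleasure each rise by 0.89 SD and passive engagement falls by 0.89 SD.

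- Passive left out: the positive composite is significant in 98% (correlation 0) to 93% (0.3) of trials.
- All three pooled: the mean shift is (0.89 + 0.89 − 0.89)/3 = 0.297 SD. Dividing by √((1 + 2ρ)/3) gives a standardised effect of 0.51 (ρ = 0) or 0.41 (ρ = 0.3). The composite is significant in 37% and 25% of trials.

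This concerns the positive half only. With distracted engagement and non-engagement unchanged, the full criterion would still not be met.

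**The case against.** Much can be said for the plan. Item means are plainly computable, so a reader who concluded that the MPES cannot be scored would go too far. Four of the five definitions sort themselves plausibly: constructive engagement and pleasure as positive, distracted engagement and non-engagement as negative. The EPWDS clause may be left over from another plan, although the documents do not say so. They show only that it is not listed, not that it was never collected. This is also one of four success criteria in a 12-person Phase 1 study.

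Two stronger readings are tempting and do not hold. A reader might infer that any single significant item could be called success, with a large chance of a false claim. Both documents join the two halves with an and, so one item cannot satisfy the criterion, and under any-and-any the null rate is about 1.4% at most. A reader might also infer that a move from passive to constructive engagement would alone count as success. It does not lower negative engagement. With only constructive engagement raised by 0.89 SD, the both-composites rule succeeds in about 1% to 2% of runs.

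What stands is narrower. The side for each domain, passive above all, and any versus all within a side remain open, and no passage settles them.

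**Conclusion.** The concern holds as an undetermined decision rule, not as an uncomputable scale or a large inflation of false positives. Following the SAP exactly gives item tests and no determinate answer on the criterion. At the same assumed effect of 0.89 SD, the chance of declaring success runs from about 41% to 57% under the strictest four-item reading to about 85% to 92% under the loosest reading that respects both halves. The placement of passive engagement can decide the positive half.

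The textual gap rests on no assumption. The percentages do: effect size, equal effects across items, correlation and alpha are all assumed, and only n = 12 comes from the documents. They show how much the missing rule matters and do not predict this trial's power.

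**What to change.** In the SAP, before analysis:

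- Delete the EPWDS clause.
- For the one-sample test, define per participant a positive composite (mean of constructive engagement and pleasure) and a negative composite (mean of distracted engagement and non-engagement). Compare each with the mean of the corresponding known item means. This requires the items to share one scale. The current text gives no MPES coding, so that should be confirmed and stated.
- Report passive engagement separately and count it on neither side.
- Declare the criterion met only if both composites differ in the favourable direction, each at two-sided 5%. No further adjustment is needed because both are required.
- Report the five items descriptively.

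In the setting above this keeps about 82% to 96% power. The joint false-positive rate is below 1% with no effect on either side, and at most 2.5% otherwise.

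The cost is SAP wording; the MPES items are already collected. Single-item significance claims are given up. Leaving passive engagement out is a choice. Another assignment would also close the gap if fixed in advance. One limit applies: Protocol 7.0 and 9.0 name an independent-samples t-test against a database. Under that test the reference SD of a composite needs the item correlations or the raw data, so the wording-only cost applies to the SAP's one-sample test.
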